All exposed aircrew personnel are males currently ranging in age from approximately 28-58 years. The normal C-123 crew composition was one pilot and one copilot/navigator (both officers) and one spray equipment console operator in the rear of the aircraft (enlisted); thus, the aircrew officer-enlisted ratio will be approximately 2:1. The inclusion of RANCH HAND support personnel (predominantly enlisted) in the study will make the overall officer-enlisted ratio approximately 1:2. While almost all officers were Caucasian, approximately 10-14% of the enlisted men were Black. Attempts will be made to identify all maintenance personnel assigned to the RANCH HAND units. Maintenance of the RANCH HAND aircraft was performed within a step-wise organizational structure. Routine daily maintenance (primary) was conducted by flight line support personnel who were often dedicated exclusively to RANCH HAND operations. More extensive maintenance (secondary) was carried out by consolidated support units at the base level, which were also responsible for non-RANCH HAND C-123s as well. Major aircraft overhauls and modification were conducted by maintenance units at Clark Air Base, Philippines. The maintenance personnel in these centralized units were not directly assigned to RANCH HAND, and their exposures to RANCH HAND C-123 aircraft and herbicide

cannot be validated. From 1962 through 1964, the primary flight line maintenance teams were dedicated to RANCH HAND aircraft and these individuals can be identified by the mechanisms described above. In 1965, flight line maintenance was performed by personnel of the centralized maintenance organization (secondary) and it may not be feasible to adequately identify these individuals from available records. After 1966, the RANCH HAND organization transferred their base of operations to a new location, and primary maintenance was once again performed by personnel assigned specifically to RANCH HAND. These individuals can again be readily identified. Thus, maintenance personnel directly assigned to RANCH HAND will be included in the study. These complexities are summarized in Table 5.

Table 5

FEASIBILITY OF IDENTIFYING AIRCRAFT MAINTENANCE
PERSONNEL (TOTAL POPULATION) EXPOSED TO HERBICIDE ORANGE

Time	Primary Maint Personnel¹	Secondary Maint Personnel²
Jan 1962-Jul 1964	Yes	No
Aug 1964-Dec 1966	Yes/No ³	No
Jan 1967-Apr 1970	Yes	No

¹individual assigned to RH; denominator known

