A review of all specialized flight units present during the RVN conflict, reveals clearly that there is no absolutely ideal control group for the RANCH HAND population. C-130 aircrew members and support personnel were selected because of sufficient population size, similar training profiles, and psychologic similarities to the RANCH HAND Group.

Total ascertainment of the C-130 population is being conducted by computer selection for specific military flying organizations, foreign country service and years of service. Over 2.3 million personnel records have already been scanned and the approximate C-130 sample size is 25,000 individuals. Aircrew members who flew C-130 aircraft in RVN during 1962-1970 will be selected as controls for the RANCH HAND aircrew population and the C-130 flight line maintenance population will be ascertained from personnel records by similar mechanisms, and will serve as the specific control population for the RANCH HAND support personnel. The proportions on active duty, and non-active duty status are expected to parallel the patterns in the exposed group.

Another possible control group, the non-RANCH HAND C-123 population, is known to be too small (approximately 3000) to provide adequate sampling flexibility and replacement under the proposed matched variable concept (see below and Section VI, I). Many of the RANCH HAND aircraft were reconfigured for transport and insecticide missions and thus, non-RANCH HAND crews responsible for these other missions, may have been exposed to significant Herbicide Orange residues in these aircraft.

Therefore, this group may not have been truly unexposed to herbicides, and was discarded as an appropriate control population. Crewmembers of C-7 transport aircraft were also considered as a potential control group; however, because of small size (1000-1200) and the fact that they served in RVN only during the post 1967 era, they were also dropped from consideration.

(a) Known or Predicted Characteristics of the Control Group

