The normal crew composition of a C-130 is three officers and two enlisted personnel. The control group will be "pure" from the standpoint of lack of occupational exposure to herbicide. The entire control group will be considered "nonvolunteer" with respect to abnormally high combat risk. While in general they will possess lifestyle characteristics and socio-economic backgrounds similar to the exposed group, their overall combat morbidity/mortality and the resultant stress influences upon general health may be slightly less than in the exposed group. For those separated and retired C-130 controls, similar proportions to the exposed group are expected to be employed in the aerospace industry. Known and estimated factors of the control and exposed populations are summarized in Table 6.

(4) Matching Procedures and Rationale

Each member of the exposed group will be computer matched to a set of C-130 controls comprised of at least 10 individuals using four variables. Since the two groups are highly selected and inherently similar with respect to many variables, very close matches are feasible. This epidemiologic design incorporates a matched concept because: (1) a matched cohort design will provide maximum test power throughout the entire study, (2) statistical intergroup comparisons may be made without normalization by four key variables known to effect symptom frequencies of interest, thus providing greater power for complex statistical testing, and (3) close matching is feasible and necessary for some of the anticipated analyses of the physical examination findings. Matches will not necessarily be rigidly maintained throughout the analytic phase, depending upon the particular analysis. It is apparent that following the match, both exposed and control populations will be very nearly identical with respect to the four influencing variables so that a replacement concept is feasible (see E below). In the event that frequent match breaks still occur, stratification techniques can be used.

Matching will be conducted for (1) age, by year of birth, and closest month possible, (2) Air Force Speciality Code (AFSC) as an absolute match, (3) length of time spent in Vietnam, to the closest six month period, and (4) race (Caucasian versus non-Caucasian) as an absolute match. These variables are listed in priority order of the match sequence. Specific rationale for these

Table 6

COMPARISON OF THE STUDY GROUP TO POSSIBLE CONTROL GROUPS BY
KNOWN AND ESTIMATED FACTORS

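### No stated rule keeps C-130 men with documented C-123 service out of the control pool, so the selection rule does not secure the claimed absence of herbicide exposure

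*Protocol*

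**What the plan says.** Protocol V.B(3) builds the control pool from personnel records by "computer selection for specific military flying organizations, foreign country service and years of service". For aircrew, "Aircrew members who flew C-130 aircraft in RVN during 1962-1970 will be selected as controls for the RANCH HAND aircrew population". For support personnel, "the C-130 flight line maintenance population will be ascertained from personnel records by similar mechanisms".

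V.B(3)(a) calls the resulting group pure "from the standpoint of lack of occupational exposure to herbicide". Table 6 enters occupational herbicide exposure for C-130 men as NO, among the known factors.

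The same V.B(3) considers the non-RANCH HAND C-123 population as an alternative control group. It rejects it for size (about 3000 men) and because "non-RANCH HAND crews responsible for these other missions, may have been exposed to significant Herbicide Orange residues in these aircraft". The conclusion there is that "this group may not have been truly unexposed to herbicides, and was discarded as an appropriate control population".

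On the maintenance side, V.B(1)(a) says that heavier work was done by "consolidated support units at the base level, which were also responsible for non-RANCH HAND C-123s as well". Table 5 adds that these secondary men may have serviced RANCH HAND aircraft and cannot be enumerated.

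**The concern.** V.B(3) treats service on non-RANCH HAND C-123s as enough doubt about exposure to help rule out a whole population as controls. The exclusion operates only at the level of the group, however. A man with one assignment on such C-123s and another on C-130s in Vietnam meets the control definition as written. The control pool is defined by the duty that admits a man, and no duty disqualifies him.

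If such men are in the pool and herbicide is harmful, they raise the control rate and pull every RANCH HAND versus control ratio toward 1, in mortality and morbidity alike. The direction matters here: Sections VI.B(1) and VIII.H already concede limited power, and Section III expects even negative findings to be used in judging compensation.

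**Working it through.** **1. Does any later step exclude these men?**

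- *Matching* (V.B(4), VI.A): age, AFSC, Vietnam tour length and race. None concerns aircraft or unit history.
- *Replacement* (V.E(3), VI.I): driven by willingness and perceived health.
- *Questionnaire* (XIII): asks organization of assignment, RANCH HAND affiliation and Vietnam exposure to herbicides, but attaches no eligibility or reclassification step for controls.
- *Stratification*: planned for domestic herbicide (VI.H) and for other pesticides (VIII.J), not for Herbicide Orange exposure among controls.
- *Data repository* (VII): lists military personnel files, flight records and unit data for study members and their controls. The information would be held, but no rule uses it to settle control status.

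No step removes such men.

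**2. Reproducing the plan's own power figure.** Table 12, row p1 = .10, p2 = .05, r = 0, α = .05, gives power .61, .75, .85 at n = 250, 350, 450 pairs. With p̄ = (p1 + p2)/2 and a one-sided, continuity-corrected, two-proportion normal test,

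power = Φ{[(p1 − p2) − 1/n − 1.645·√(2p̄(1 − p̄)/n)] / √([p1(1 − p1) + p2(1 − p2)]/n)}

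This gives .621, .766, .860, within 2 points of each entry. Not every row of Table 12 reproduces this closely (for .20 v .10 at n = 450 the formula gives .994 against .97), so it is used only for this row.

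**3. Size of the dilution.** Let c be the share of controls who were exposed and f the share of the RANCH HAND excess risk that they carry. The protocol gives neither; both are assumptions.

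Control rate: p2′ = p2 + c·f·(p1 − p2). Apparent RR = p1/p2′ = RR/[1 + c·f·(RR − 1)].

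Example, c = 5%, f = 1: p2′ = .05 + .05 × .05 = .0525, and .10/.0525 = 1.90.

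| c | RR, f = 1 | power, f = 1 | RR, f = 0.5 | power, f = 0.5 |
|---|---|---|---|---|
| 0 | 2.00 | .860 | 2.00 | .860 |
| 1% | 1.98 | .853 | 1.99 | .856 |
| 2% | 1.96 | .845 | 1.98 | .853 |
| 5% | 1.90 | .821 | 1.95 | .841 |
| 12% | 1.79 | .756 | 1.89 | .812 |

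(n = 450 pairs, p1 = .10, p2 = .05.) A two-sided test without continuity correction starts lower but moves similarly: .814 at c = 0 and .767 at c = 5%, f = 1.

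For a true RR of 3 (.03 v .01) with f = 1, c = 1%, 2%, 5% reads 2.94, 2.88, 2.73.

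**4. How much overlap each c would need.** Suppose the contaminated men come only from the roughly 3000 non-RANCH HAND C-123 men and controls are drawn evenly from the pool of 25,000.

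- c = 1% is 250 men, 250/3000 = 8% of that population.
- c = 2% is 500 men, 17%.
- c = 5% is 1250 men, 42%.
- c = 12% is 3000/25,000, which requires every one of them to be in the C-130 pool.

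**The case against.** The strongest reply is that non-exposure is part of the definition. V.B(3) is headed as a group not exposed to Herbicide Orange, V.B(3)(a) repeats it and Table 6 records it. The record filter would then be only an operational detail. This does not close the gap: a heading does not tell whoever runs the selection which men to drop, and Table 6 describes groups by aircraft type rather than by each man's assignment history.

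Other parts of the reply stand and limit the point.

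- *Dual service is not documented.* A reader might infer that the control group is in fact contaminated. The protocol leaves this possible but does not show it. The consolidated units are described as servicing C-123s, whereas support controls come from C-130 flight line maintenance. Identified RANCH HAND men would presumably be placed in the exposed cohort.
- *Matching on tour length.* A reader might infer that it concentrates men with a second assignment among the controls. Nothing in the protocol says so, and V.G gives a one-year tour for most RANCH HAND men.
- *Dead controls.* A reader might infer that exposure in dead controls could never be found. Section VII plans personnel, flight and unit data, none of which needs an interview.
- *Size.* Giving contaminated controls the full RANCH HAND excess risk is a worst case, since the plan says only that C-123 crews may have met residues.
- *Reach of any filter.* Drum handlers had no personnel designator (V.B(2)), and some maintenance men cannot be identified from records (V.B(1)(a), Table 5).
- *A second line of evidence.* Regression on the exposure index within RANCH HAND (V.G, VI.H) uses no controls and is unaffected.

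**Conclusion.** The point holds as a gap between rule and claim. Followed as written, V.B(3) can admit to the control group men whom the same section regards as possibly exposed, and no later step removes them. The stated purity is therefore asserted and not secured by the rule.

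The consequence is a bias toward no effect, probably small. At 1% to 5% contamination a true RR of 2 reads 1.98 to 1.90 with full excess risk, and 1.99 to 1.95 with half. Power in the Table 12 case falls by at most about 4 points over that range (.860 to .821). This rests on assumed values of c and f, on controls drawn evenly from the pool, and on dual-service men not differing from other controls in other respects that affect risk. It does not support saying that the comparison is invalid or that contamination has been demonstrated. It does support adding a rule before matching, while that is still simple.

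**What to change.** 1. Before matching, use the personnel, flight and unit records named in V.B(3) and VII to exclude from the C-130 pool any man with a documented assignment to a C-123 unit (RANCH HAND or other) or a spray unit. Where records permit, also exclude men assigned to a consolidated maintenance unit that serviced C-123s.
2. Decide exclusion from records only, by the same rule for living and dead candidates, so that self-report and vital status cannot influence who becomes a control.
3. In V.B(3)(a), replace 'pure' with 'no documented C-123 or spray-unit assignment', and bring Table 6 into line. State that drum handlers and some secondary maintenance men cannot be identified from records and may remain.
4. Use controls' questionnaire answers on Vietnam herbicide exposure (XIII) only in a sensitivity analysis.

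The cost is an added filter on records already being searched, and a somewhat smaller pool. Overall there is room: 25,000 men against about 10 × 1200 = 12,000 controls. That total does not show whether each cell of absolute AFSC and race match with close age and tour match still holds ten men. Supply in those cells is unknown and should be counted once the filter has been run.

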Figure 1. Mortality Analysis Cohorts

RH COHORT	CONTROL COHORTS					
	C ₁ _____ C ₁₀					
E ₁	C _{1,1}	C _{1,2}	C _{1,3}	C _{1,4}	C _{1,10}
E ₂	C _{2,1}	C _{2,2}	C _{2,3}	C _{2,4}	C _{2,10}
E ₃	C _{3,1}	C _{3,2}	C _{3,3}	C _{3,4}	C _{3,10}
E ₄	C _{4,1}	C _{4,2}	C _{4,3}	C _{4,4}	C _{4,10}
.
.
.
E _j	C _{j,1}	C _{j,2}	C _{j,3}	C _{j,4}	C _{j,10}

(b) Questionnaire, Physical Examination and Follow-up Study

Each living exposed subject and a randomly selected individual from his set of five mortality controls will be included in the questionnaire and physical examination phases of the study. If this primary control is deceased, unaccountable, or unwilling to participate in the morbidity and follow-up studies, another control will be selected and so on until a willing subject is found (Figure 2). Since the control's vital status and volunteerism should be independent of the matching sequence, many primary controls should enter the study. The remaining members of the control set will be used as replacement candidates for possible use later in the study (see section E below). All replacement controls will be clearly identified for the purposes of subset analysis so that population differences, if any, between the first randomly assigned selectees (noncompliant) and the replacements (compliant) can be assessed.

Figure 2. Selection Procedure for the Questionnaire, Physical Examination, and Follow-up Study

- † Deceased
- Unwilling
- * Volunteer
- ** Replacement Candidates

C. Mortality Study

(1) Introduction

The mortality, morbidity, and follow-up studies are components of a "non-concurrent" prospective study used in the observation of a specially exposed group or industrial population starting from some date in the past. The initial exposures occurred 8-17 years ago and varied in intensity and duration from one RANCH HAND member to another. Access to employment, medical and other

types of records is an obvious requisite for such a study. The classical "case-control", retrospective study is not operative in this protocol due to the lack of defined clinical endpoints. The mortality study will be conducted in two phases; a review of past mortality, and a continuing assessment of the death experience in the exposed and control cohorts over the duration of the RANCH HAND II project.

(2) Data Collection Methods

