The mortality status of the exposed cohort and the randomly selected controls will be ascertained using multiple techniques including; telephone interviews with subjects or their families, a review of Death Benefits claims filed with the VA, acquisition of death certificates on all known deceased individuals and reviews of autopsy reports and medical records whenever possible.

D. Morbidity Study

(1) General Considerations

A vigorous attempt to determine the morbidity experience of all exposed subjects and their primary controls will be undertaken using questionnaires, indepth personal interviews, and physical examinations. The schedule and method of contact with the study subjects is depicted in the Appendix, Table A-5.

(2) Questionnaire Methods

All exposed members and their matched primary controls will be offered a comprehensive personal and family health questionnaire via telephone. The telephone questionnaire is an important part of this study because non-compliance rates for the physical examination and its face-to-face interview are expected to be substantially greater than non-compliance with the telephone questionnaire. As depicted in the Appendix, Figure A-2, only an estimated 40% of the RANCH HAND population will participate in the examination, while 65% will respond to the telephone questionnaire. The information collected by questionnaire from these additional 309 individuals and their controls will provide valuable morbidity data which would otherwise be lost. The questionnaire (see Section XIII) will emphasize identification data, RVN tour history, dermatologic conditions, neuropsychiatric conditions, fertility aberrations, genetic defects in offspring, sensory defects, and personality factors, including assessments of risk-taking behavior. A review of medical systems will be included in the questionnaire, and will inventory symptoms prior to, during, and after duty in RVN as well as those currently manifested. The questionnaire will be limited to a 30-45 minute telephonic interaction with participants, and it will take 10 to 12 months to complete all initial questionnaires on both groups. It may be necessary to conduct the questionnaire in two telephone sessions to minimize fatigue and maximize response. The

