questionnaire will be "field-tested" on a group of 25 to 30 former Air Force pilots with RVN combat experience. Specific questions on the questionnaire will be directed to verifiable information, wherever possible. Specific response verification and bias indicator questions (nonsense symptoms), and indicators of risk-taking behavior are being developed. They will be added and appropriately sequenced immediately prior to the start of the study. Questionnaire data will be cross-linked and integrated with medical record information and physical examination findings. Questionnaire data from individuals not completing all phases of the study will not be discarded, but will be incorporated within the entire data base where statistically appropriate. Each participant will be asked to sign release forms so that all civilian health records, including those of dependents, can be obtained and reviewed as necessary. Federal health records on all family members on file in the NPRC will be retrieved. For retired members, and separated members with VA privileges, all available VA medical records will be obtained. All retrieved medical records will be reviewed, scored, compared to questionnaire data for reliability, and then be entered into a repository system. Identified participants who are non-responsive to questionnaire will be pursued to determine status, disinterest, moribund state or death, etc. These individuals will be cross-referenced in other federal record systems in an attempt to achieve total ascertainment. Death certificates and autopsy reports will be retrieved on all dead exposed and matched control subjects for the mortality analysis. Birth/death certificates will be sought for all offspring, born subsequent to the study subject's RVN duty.

(3) Physical Examination

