A voluntary comprehensive physical examination will be offered to all individuals in both the exposed and primary control groups. The condition for entry into the examination phase of the study will be the completion of the baseline questionnaire. In the event that the primary control does not complete both the questionnaire and the physical examination, a replacement will be selected from the control set (See Figure 2). Consequently, "person-months" of observation will be used in the statistical analysis. Statistical testing will be conducted by a variety of techniques on both questionnaire and examination findings (see VI, Statistical Methodology below). At the time of physical examination, an extensive face-to-face interview will be conducted. A standardized protocol will be used to insure comparability of interview data. This will provide cross-reference data to the initial questionnaire and to medical record data, if retrievable. Specific response verification and bias indicator questions will be included in the interview as well.

(4) Examination Parameters

A comprehensive physical examination will be conducted on all willing participants. The examination will be structured as outlined below and in Section XIV.

Physical Examination Profile

General Physical Examination	Hemoglobin	CPK
FBS, 2 Hr Post Prandial	Hematocrit	ECG
Urinalysis	White Blood Cell Count	Chest X-Ray
BUN/Creatinine	Platelet Count	VDRL/FTA
Cholesterol/HDL Cholesterol	RBC Indices	
Triglycerides	Sedimentation Rate	
Serum Protein	Cortisol Differential	
Electrophoresis	Thyroid Profile (RIA)	

Dermatologic Examination

- Urine Porphyrins
- Urine Porphobilinogen
- Delta-aminolevulinic Acid

Neuro-Psychiatric Examination

General Neurologic Examination	Nerve Conduction
Psychological Battery	Velocities

- MMPI
- WAIS
- WRAT
- Halstead-Reitan
- Wechsler Memory Scale Subtests
- Cornell Index

Reproductive Examination

- LH, FSH, Testosterone
- Semen Analysis

Neoplastic/Hepatic Examination

SGOT	Alkaline Phosphatase
SGPT	LDH (Isoenzymes if elevated)
GGTP	

Additional Studies (Individuals with abnormal history or examination)

Karyotyping	Anti-Nuclear Antibody
Hepatitis Antigens/ Antibodies (A and B)	Immuno-electrophoresis
Additional Consultations as Required	Monilia Skin Test
	Quantitative Immunoglobulins
	Bilateral profile and full- face photographs

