Loss of participants over time adversely affects any epidemiologic study in two ways. As the sizes of the study groups decrease, statistical power also declines, and bias is injected into the study if losses are not randomly distributed in the study populations. It is reasonable to assume that in this study, losses will be non-random with greater non-compliance among individuals who perceive their health as "well," since there is less incentive for this group to continue participation. As shown in Figure 3, such a differential pattern of loss will alter the population and skew the frequency distribution curve.

Most previous epidemiologic studies have approached the problem of declining statistical power by beginning the study with multiple controls per exposed subject, and passively allowing attrition to occur throughout the study period. However, this approach does not address the problem of bias. This study will take an active approach to both of these problems by using a replacement concept. As a control is lost to study, a replacement will be chosen from the original set of 10 matched controls. The replacement will be selected from the control set, and will have a perception of health similar to that of the lost control (Figure 4). The replacement strategy will maintain statistical power and the integrity of the matched design despite loss to study in the control group, and will correct anticipated bias while minimizing the number of required physical examinations.

[figure not shown]
At the initiation of the follow-up study, loss of an exposed member will not be cause to cease surveillance of his primary matched control. In the event of a control loss (for reasons other than death), another control from the set will be brought to study (Figure 5), the comprehensive questionnaire will be administered, and a baseline physical examination performed. Medical data

EFFECT OF NON-RANDOM LOSS TO STUDY IN THE CONTROL POPULATION

- IF CONTROL LOSSES ARE ILL, A SPURIOUS EFFECT IS ATTRIBUTED TO HERBICIDE EXPOSURE.
- IF CONTROL LOSSES ARE WELL, A TRUE/VALID HEALTH EFFECT IS DILUTED.

ANALYSIS OF THE REPLACEMENT STRATEGY

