The USAF is committed to expending maximal effort to encourage participation. Loss to study problems in the study participants will be avoided as much as possible by detailed and exhaustive efforts to contact and followup each identified participant. NON-PARTICIPANTS WILL BE STRONGLY ENCOURAGED TO RECONSIDER THEIR INITIAL DECISIONS. Design considerations have been made to minimize loss to study in both the exposed and control populations. Although the USAF can not compensate study subjects for lost wages during the physical examination, transportation costs, per diem, and lodging costs will be reimbursed.

The replacement concept will help to counteract the decrement in statistical power, and offset the bias created by differential patterns of loss. The exposed group is already of maximum size and cannot be increased, but non-compliant controls can be replaced. This will maximize the degree of pairing between the two study groups. If a non-compliant control is replaced by a control with a similar perception of his own state of health, the alteration of the control group distribution is offset; (i.e., an "ill" control is replaced with an "ill" individual, and a "well" control with another "well" individual.) This concept of replacement, coupled with extensive efforts to encourage compliance will minimize losses to study and offset the adverse effects of those losses that do occur.

H. Statistical Power Limitations

(1) Problem

As discussed above, statistical power considerations are heavily dependent on loss to study rates. Since the design of the study is also limited by the small exposed population, statistical power for identifying the relative risk of an uncommon disease or symptom-complex ($<1/100$) is very low ($<.50$), (See Section VI F). This study will, to a greater extent, be able to detect increased risks only in common diseases or symptom-complexes ($>1/100$).

(2) Discussion

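### A control keeps his place in the pair only if he is also examined, while a RANCH HAND man need not be, so on the plain reading the questionnaire comparison sets questionnaire responders against examination completers

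*Protocol*

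**What the plan says.** **Control side.** Section V.D(3) states that if the "primary control does not complete both the questionnaire and the physical examination, a replacement will be selected from the control set". Section V.B(5)(b) has the same sense: if the primary control is "unwilling to participate in the morbidity and follow-up studies, another control will be selected", and so on until a willing man is found. Section VI.A adds that a single mortality-study control serves each RANCH HAND man in both the questionnaire and the examination phase.

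**Exposed side.** Section VIII.G states: "The exposed group is already of maximum size and cannot be increased, but non-compliant controls can be replaced". Section V.D(2) expects that "only an estimated 40% of the RANCH HAND population will participate in the examination, while 65% will respond to the telephone questionnaire", and continues: "The information collected by questionnaire from these additional 309 individuals and their controls will provide valuable morbidity data which would otherwise be lost".

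**Partial data.** Section V.D(2) also says: "Questionnaire data from individuals not completing all phases of the study will not be discarded". They are to be incorporated where that is statistically appropriate, with no further rule.

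**Planned safeguards.** Sections V.E(3), VI.I and VIII.G call for replacements with a similar perception of health. Sections V.B(5)(b), VI.A and VI.I flag the replacements, compare them with the lost controls and add an analysis without them. Section VI.I analyses intact pairs first.

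**The concern.** Section VI.A builds the questionnaire phase on the ratio s_R/s_C. For that ratio to reflect exposure, both rates should come from men at the same level of volunteering. The replacement rule ties the control's place to a second, more demanding step, and the exposed man's place is not tied to it.

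Attendance is expected to depend on health. Section V.E(3) anticipates "greater non-compliance among individuals who perceive their health as" well. If so, examination completers report more symptoms than questionnaire responders as a whole, s_C is too high and a true symptom excess is diluted. The questionnaire is the larger of the two morbidity phases, so the loss falls where the study has most men. The over-reporting check in section VI.A, which contrasts f_R/s_R with f_C/s_C, takes on the same imbalance.

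**Working it through.** **1. The plan's own figure.** Questionnaire-only RANCH HAND men = (0.65 − 0.40) × population. With the 1,200 of section V.B(1) this is 300, against the stated 309 (implied base 309/0.25 = 1,236). The figure reproduces within 3%. On the base of about 1,000 in section VI.B(1) it would be 250, which does not.

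**2. Composition of the two sides.** Among exposed questionnaire responders, 0.40/0.65 = 61.5% are examinees and 0.25/0.65 = 38.5% are questionnaire-only. If the pair's control must complete both steps, 100% of controls are examinees.

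**3. How often the rule would act.** Table 14 assumes P1 = 0.70. At the first examination it shows 318 first-selected controls, 967 − 318 = 649 replacements and 33 unmatched, out of 1,000. P1 covers every cause of non-compliance, so not all 649 are men who answered the questionnaire and then declined the examination. The protocol gives no control questionnaire rate from which to separate them.

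**4. Size of the distortion.** The protocol gives neither symptom rates nor their link to attendance, so these are assumptions. Let s = 0.20 be symptomatic among questionnaire responders in both groups, let symptomatic men be k times as likely to attend, and let health matching do nothing.

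Rate in completers = s·k / (s·k + 1 − s)

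| k | Control rate | Null ratio reads | True ratio of 1.5 reads |
|---|---|---|---|
| 1.25 | 0.25/1.05 = 0.238 | 0.20/0.238 = 0.84 | 0.30/0.238 = 1.26 |
| 1.5 | 0.30/1.10 = 0.273 | 0.20/0.273 = 0.73 | 0.30/0.273 = 1.10 |

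**5. Cross-check with the 61.5/38.5 mix.** Again with no herbicide effect:
- 15% symptomatic in examinees and 10% in questionnaire-only men: s_R = 0.615 × 0.15 + 0.385 × 0.10 = 0.131, and the ratio is 0.131/0.15 = 0.87.
- 20% and 10%: s_R = 0.1615, and the ratio is 0.1615/0.20 = 0.81.
- Opposite direction, 10% and 15%: s_R = 0.119, and the ratio is 0.119/0.10 = 1.19. With 10% and 12% it is 1.08, and with 10% and 20% it is 1.39.

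**6. Over-reporting ratio.** In the 20% and 10% case, with equal findings rates in examinees, f_R/s_R is 0.20/0.1615 = 1.24 times f_C/s_C without any group difference. A low f_R/s_R is the plan's signal of over-reporting, so this would mask it.

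**7. Do the planned analyses remove it?** If an intact pair is one whose control was not replaced, that control has by rule completed both steps while his RANCH HAND partner may have answered the questionnaire only. The intact-pair analysis and the analysis without replacements then carry the same asymmetry. Health matching cannot help there, because those analyses contain no replacements. Only if intact also required the RANCH HAND man to be examined would the sides agree. The protocol does not say so, and the 309 would then drop out of that analysis.

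**The case against.** The strongest reply is that replacing a man is not the same as discarding his questionnaire. Section V.D(2) keeps partial data and counts the 309 men together with their controls, and section VI.A defines the comparison on living RANCH HAND men and primary matched controls, not on examination completers. A reader might therefore infer too much in claiming that the protocol drops decliners' questionnaires. It does not: the records are retained and another use is permitted. What remains is that they have no assigned role, while sections V.D(3) and VI.A put a different man in the pair.

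It can also be said that the choice of record belongs in an analysis plan, which is not at hand. That would carry weight if the protocol were silent. Here it states a rule which, followed as written, gives non-comparable rates.

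Health-matched replacement is a real safeguard and is required in several sections, although V.B(5)(b) and V.D(3) do not repeat it. It would shrink the bias in the all-pairs analysis, but only as far as the health factors capture symptoms. Those under consideration in Table 15 are three two-level items: self-rated health, long-term care and absenteeism.

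A reader might also infer that a symptom excess will certainly be hidden, and by a large factor. The documents do not support this. Section VIII.D names fear of career harm from abnormal results, particularly among active pilots, and section VIII.G considers loss of ill controls. Either would reverse the bias. Nor is a doubling of attendance among symptomatic men (k = 2) feasible at the protocol's exposed-side ratio: with s = 0.20, symptomatic attendance would be 2 × 0.615/1.2, about 103%.

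Figures 2, 5 and A-2 are not visible in the text at hand and may bear on the rule.

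**Conclusion.** The concern holds in a limited form. Read together, sections V.D(3) and VI.A make the pair's control a man who completes both steps, while 309 questionnaire-only RANCH HAND men, about 38% of exposed responders, remain in the comparison. On that plain reading s_R and s_C come from different levels of participation, and the intact-pair analysis does not cure it.

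Under the assumptions in step 4 a null ratio reads about 0.84 to 0.73. These are illustrative upper bounds: they take every decliner as absent from s_C and give health matching no credit. The direction is towards dilution if well men decline more often, as section V.E(3) expects, and reverses if ill men or pilots do. The asymmetry rests on the text. Its size rests on assumptions that the protocol cannot settle.

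**What to change.** In V.D(3) and VI.A, state that the first control in random order who completes the questionnaire is the questionnaire control for every s_R/s_C comparison, whatever his examination status. A replacement recruited because of an examination refusal enters the examination comparisons only. His own questionnaire still classifies him as symptomatic or not for f_CS and for the corresponding rate in asymptomatic controls, but does not count in s_C. For the f/s ratios and the intact-pair questionnaire analyses, apply the same participation level to both groups.

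The cost is one rule and one flag in the master file, with no extra contacts, since replacements are already labelled. Some imbalance can remain if controls differ from RANCH HAND men in willingness. In the 20% and 10% case, with 30% of controls examined (from P1) and an assumed 50% to 60% answering the questionnaire, s_C is 0.16 to 0.15. The null ratio is then 0.1615/0.16 = 1.01 to 0.1615/0.15 = 1.08, instead of 0.81. Limiting both groups to examinees gives 1.00 under the same assumptions and is a useful companion analysis.
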